**AMENDMENT HISTORY**

SAP History VAC18193RSV2001	
Document Type and File Name	Issue Date
Initial Statistical Analysis Plan VAC18193RSV2001_SAP	18-July-2019
Amended Statistical Analysis Plan VAC18193RSV2001_SAP Amendment 1	1-April-2020
Amended Statistical Analysis Plan VAC18193RSV2001_SAP Amendment 2	3-April-2020
Amended Statistical Analysis Plan VAC18193RSV2001_SAP Amendment 3	29- May -2020
Amended Statistical Analysis Plan VAC18193RSV2001_SAP Amendment 4	11-January-2021
Amended Statistical Analysis Plan VAC18193RSV2001_SAP Amendment 5	20-April-2021
Amended Statistical Analysis Plan VAC18193RSV2001_SAP Amendment 6	23-July-2021
Amended Statistical Analysis Plan VAC18193RSV2001_SAP Amendment 7	11-July-2022

**Amendment 7**

Following CBER comments and to align with the Phase 3 studies, the follow-up time, for the End of Efficacy analysis will start from Day 14 Post-Dose instead of Day of Vaccination. Details on the analysis of potential AESIs determined programmatically are included. All AESI analyses will be presented by phase as well as by time interval. The definitions of these time intervals were added. Additionally, for solicited AEs, the denominator for the percentages will be the number of participants with data assessed by the PI in the considered population and phase for a certain regimen (incidence per 100 participants/phase) and risk level.

The Per Protocol Efficacy Set and the follow-up time were updated for the analyses across the three RSV seasons. Analyses focusing on season two and three were added as well. Further, the emergency department visit details were updated to specify that only emergent MRU will be retained. The scoring of the Patient Global Impression of Health (PGI-H) was updated to align with the Phase 3 studies. Additionally, details on the approximate ARI surveillance compliance were added for the analysis across RSV seasons. Severe acute respiratory syndrome coronavirus 2 (SARS-CoV-2) was added to the list of respiratory viruses used to define coinfections.

Clarifications were made to the section on the calculation of an ARI duration and determination of new onset or worsening. Information was added to Section 5.1. regarding subject information. And some exploratory immunogenicity assays were added.

The footnote regarding the use of a relative day 365/day 730 was updated to only use such a relative date when no scheduled/unscheduled visit is present and when there is still ARI surveillance present after this date.

**Amendment 6** 23-July-2021

**The primary reason for the amendment:** The SAP was amended to align with Protocol Amendment 5 and 6 and to include information on the statistical analysis of the third RSV season and the additional Revaccination Subcohorts. Additionally, very rare events of thrombosis with thrombocytopenia syndrome (TTS) will be followed as an AESI in the Revaccination Subcohorts of this study. The visit window of Day 365 was updated to align with the CTP amendment.

Clarification and/or updates on the analysis were added in the following sections:

- 1.2. Study design updated to include the Revaccination Subcohorts
- 1.6. Changes to Planned Analysis
- 2.1.1. Phase definitions
- 2.1.2. Immunogenicity visit windows
- 2.3. Analysis Sets
- 3.3. Analysis 28 Days Post Second Vaccination in Revaccination Subcohorts A, B, C and D
- 3.4. End of Season 2 Analysis
- 3.5. Analysis of Revaccination Subcohorts A and B, when Revaccination Subcohorts 2A and

2B have reached the 28 Day Post Third Vaccination Timepoint

- 3.6. End of Efficacy Study Analysis
- 3.7. Final Analysis of Revaccination Subcohorts (A, B, C and D)
- 4.1.1. Demographics and Baseline Characteristics
- 4.1.4. Concomitant Medications
- 4.17. Post-hoc Analyses
- Section 5: Revaccination Subcohorts and Second and Third RSV Season Analysis
- Attachment 1: Transforming Solicited AEs into Analysis Format
- Attachment 10: Clinically Relevant Complication AE terms

**Amendment 5** 20-April-2021

Clarifications were added in the ‘Phase definitions’ section.

**Amendment 4** 11-January-2021

**The primary reason for the amendment:** The SAP was amended to align with the Protocol Amendment 4 and to include information on the statistical analysis of the second RSV season.

Clarification and/or updates on the analysis were added in the following sections:

- Study design updated to include revaccination subcohort
- Phase definitions
- Analysis Sets
- Season 2 efficacy analysis
- Combination of adverse events
- Immunogenicity visit windows

Moreover, at Section [4.9.1](#) and [4.10.1](#) the vaccine efficacy analysis for the clinically relevant diseases and new therapeutic interventions was updated to include an exact Poisson test, instead of an exact Binomial one, to align with the analysis of the primary endpoint.

The exact Binomial and the exact Poisson provide nearly identical vaccine efficacies and confidence intervals (the difference is less than 0.5%).

Finally, tetrachoric and polychoric correlations were used in order to evaluate the correlation of the RiiQ symptoms collected at the site and by the participant, instead of Kendall’s rank correlation coefficient .

Other minor corrections in punctuation were made throughout the document.

---

**Amendment 3** (29 May 2020)

**The primary reason for the amendment:** The SAP was amended:

- To align with CTP amendment 3 (removal of the year 1 vaccination in the description of the design, G-ELISA is now an exploratory immunogenicity endpoint)
- to remove emergency department visits from the hospitalization definition
- to update the definition of a treatment - emergent medical resource
- to add details on how to calculate the percentage of compliance with RiiQ assessments

Some additional small clarifications were made throughout the document.

---

**Amendment 2** (3 April 2020)

**The primary reason for the amendment:** The SAP was amended to clarify that RT-PCR results from samples that were out of stability are excluded from the analysis, regardless if they were RSV positive or RSV negative.

- For the primary endpoint, those samples received out of stability are not taken into account
- In the sensitivity analysis based on the FAS, those samples that were out of stability are included if they tested RSV positive
- For the multiple imputations model, samples received out of stability are considered missing.

**Amendment 1** (1 April 2020)

**The primary reason for the amendment:** The SAP was amended to align with the Protocol Amendment 2. Moreover, clarification on the analysis were added:

- The definition of the baseline
- EMA and CEC exploratory endpoints added
- Handling missing RiiQ items in calculations of total scores and frailty indexes
- Conditional power algorithm added
- New Concomitant medication definition added
- Handling missing oxygen saturation and respiratory rate in calculation of symptoms added
- The end of the ARI surveillance was updated based on the amended Protocol.

Other minor corrections in punctuation were made throughout the document.

---

**ABBREVIATIONS**

AE	adverse event
AESI	Adverse event of special interest
ARI	Acute respiratory infection
AUC	Area under the curve
BMI	body mass index
CI	confidence interval
CP	Conditional power
CDC	Centers for Disease Control and Prevention
CKD	Chronic Kidney Disease
CRF	case report form
CSR	Clinical Study Report
DPS	Data presentation specifications
ECG	Electrocardiogram
eCRF	electronic case report form
ELISA	Enzyme-linked immunosorbent assay
ELISpot	enzyme-linked immunospot
FA	Full Analysis Set
ePRO	electronic patient-reported outcome
F protein	fusion protein
FDA	Food and Drug Administration
IA	Interim Analysis
ICH	International Conference on Harmonization
IDMC	Independent Data Monitoring Committee
IF	Information Fraction
IF	Information Fraction
IF	Information fraction
ITT	Intent-to-Treat
ICS	Intracellular Cytokine Staining
IU/ml	International units per milliliter
IVRS	interactive voice response system
LLOQ	lower limit of quantification
LLOQ	lower limit of quantification
LOCF	last observation carried forward
LRTD	lower respiratory tract disease
LRTI	lower respiratory tract infection
MedDRA	Medical Dictionary for Regulatory Activities
MPD	Major Protocol Deviation
NA	Not Applicable
NH	Northern hemisphere
PA	Primary Analysis
PD	Pharmacodynamic
PI	principal investigator
PK	pharmacokinetic(s)
PP	Per Protocol
POC	Proof of concept
PPE	Per protocol efficacy
PPI	Per protocol immunogenicity
RiiQ	Respiratory Infection Intensity and Impact Questionnaire
RR	Relative ratio
RSV	respiratory syncytial virus
RT-PCR	reverse transcriptase polymerase chain reaction
RWE	Real world evidence
SAE	serious adverse event
SAP	Statistical Analysis Plan
SD	standard deviation
TLF	Tables, Listings and Figures

TTS	Thrombosis with Thrombocytopenia Syndrome
SH	Southern hemisphere
ULOQ	upper limit of quantification
VE	Vaccine Efficacy

## 1. INTRODUCTION

This is the Statistical Analysis Plan (SAP) applicable for the VAC18193RSV2001 proof-of-concept (POC) study. This SAP is applicable for all analyses up to the end of the third RSV season analysis, as well as for all analyses regarding the Revaccination Subcohorts as described in the clinical trial protocol (CTP) under Section 11.12. Note that the validation of the PRO questionnaires and the correlate of protection analysis will be described in separate SAPs.

This document contains all information needed for performing a full efficacy, safety, and immunogenicity analysis. The tables, listings, and figures (TLF) required for each analysis will be described in separate data presentation specifications (DPS) documents.

### 1.1. Study Objectives

Please refer to Section 2.1 in the CTP.

### 1.2. Study Design

This is a multi-center, randomized, double-blind, placebo-controlled Phase 2b proof-of-concept study in male and female participants aged  $\geq 65$  years who are in stable health. A target of up to 5,800 participants (Cohort 1) will be enrolled and randomized in parallel in a 1:1 ratio to 1 of 2 groups to receive Ad26.RSV.preF/RSV preF protein mixture or placebo intramuscularly ([Table 1](#)).

At Day 365, a subcohort of Cohort 1 participants will be identified and will be revaccinated, to assess safety and immunogenicity of a second vaccination. This Revaccination Subcohort (N=240) will consist of at least 120 participants who received active study vaccine on Day 1 and 120 participants who received placebo on Day 1, and who have given informed consent for the additional study procedures. Additional Revaccination Subcohorts were implemented. Participants in these additional Revaccination Subcohorts will receive a revaccination with active study vaccine at 2, 3, or 4 years after the first vaccination to assess the safety and immunogenicity of revaccination with Ad26.RSV.preF/RSV preF protein mixture or with the individual vaccine components as indicated in the table below ([Table 1](#)).

During all 3 RSV seasons, as well as between the second and third RSV season, participants in cohort 1 will be followed-up twice per week to monitor for symptoms that could indicate an ARI. For participants in the Revaccination Subcohorts, follow-up of ARIs will stop at the end of the second RSV season for Subcohort A, at the Day 730 (Month 24) visit for Subcohort B, and at the latest at the end of the third RSV season for Subcohorts C and D. Please refer to Section 3.1 in the CTP for further details.

**Table 1: Study Design: VAC18193RSV2001**

Cohort/Group/ Subcohort	Day 1 Vaccination	Day 365 (Month 12) Revaccination	Month 24 Revaccination	Month 36 Revaccination	Month 48 Revaccination
		(Amendment 4)	(Amendment 5)		
Cohort 1a,b N=5,800					
Group 1 N=2,900	Active vaccine mixture				
	Safety Subsetc (N=350) Immuno Subsetc (N=100)				
Revaccination Subcohort 1Ac (N=120)	Active vaccine mixture	Active vaccine mixture			
Revaccination Subcohort 1Bc (N=135)	Active vaccine mixture		Active vaccine mixture		
Revaccination Subcohort 1Cc,d (N=120)	Active vaccine mixture			Active vaccine mixture	
Revaccination Subcohort 1Dc,d (N=120)	Active vaccine mixture				Active vaccine mixture
Group 2 N=2,900	Placebo				
	Safety Subsetc (N=350) Immuno Subsetc (N=100)				
Revaccination Subcohort 2Ac (N=120)	Placebo	Active vaccine mixture	Ad26.RSV.preF alone (N=40)		
			RSV preF protein alone (N=40)		
			Active vaccine mixture (N=40)		
Revaccination Subcohort 2Bc (N=135)	Placebo		Active vaccine mixture	Ad26.RSV.preF alone (N=45)	
				RSV preF protein alone (N=45)	
				Active vaccine mixture (N=45)	
Revaccination Subcohort 2Cc,d (N=120)	Placebo			Active vaccine mixture	
Revaccination Subcohort 2Dc,d (N=120)	Placebo				Active vaccine mixture

Active vaccine mixture refers to Ad26.RSV.preF (1×10^11 vp)/RSV preF protein (150 µg) administered as a single injection. Ad26.RSV.preF alone refers to Ad26.RSV.preF at a dose of 1×10^11 vp. RSV preF protein alone refers to RSV preF protein at a dose of 150 µg.

a If 5,500 or more participants are enrolled from the NH, no additional participants from the SH will be enrolled (see Section 11.2 in the CTP). In addition, if the number of participants enrolled in the NH is less than 5,500 but 18 or more RT-PCR-confirmed RSV-mediated LRTD events (using Case Definition #2) are observed in the NH before opening sites in the

**Table 1: Study Design: VAC18193RSV2001**

Cohort/Group/ Subcohort	Day 1 Vaccination	Day 365 (Month 12) Revaccination	Month 24 Revaccination	Month 36 Revaccination	Month 48 Revaccination
		(Amendment 4)	(Amendment 5)		

SH, no sites will be opened in the SH and the study will be performed as a NH study only (see Section 11.12 in the CTP).

b The study progression beyond the first year is dependent on results obtained at the end of the first NH RSV season.

c Participants who provided separate informed consent.

d The study will continue with Revaccination Subcohorts C and D depending on the 28-day post second vaccination analysis results from Revaccination Subcohort B.

LRTD=lower respiratory tract disease, NH=Northern Hemisphere, SH=Southern Hemisphere, vp=viral particles

### 1.3. Statistical Hypotheses for Study Objectives

The study is designed to test the primary hypothesis of vaccine efficacy (VE) in the Per-protocol Efficacy (PPE) population.

- The null hypothesis is that the VE for each of the 3 primary endpoints (see Section 4.4.2) is  $\leq 0\%$
- The alternative hypothesis is that the VE for at least one of the primary endpoints is  $> 0\%$

No formal hypothesis on safety and immunogenicity will be tested.

### 1.4. Sample Size Justification

Please refer to Section 11.2 in the CTP.

### 1.5. Randomization and Blinding

Please refer to Section 5 in the CTP.

### 1.6. Changes to Planned Analysis

Additional details were added for several exploratory endpoints.

Moreover, all RT-PCR confirmed RSV cases, during the first RSV season will be evaluated by a Clinical Evaluation Committee (CEC) and classified as mild, moderate, or severe RT-PCR confirmed RSV-mediated diseases. See CEC Charter (EDMS-ERI-51904526) for further details on the CEC responsibilities. Based on the CEC evaluation the following exploratory endpoints were added:

- first occurrence of an RT-PCR confirmed RSV LRI assessed as at least mild by the CEC
- first occurrence of an RT-PCR confirmed RSV LRI assessed as at least moderate by the CEC.
- first occurrence of an RT-PCR confirmed RSV LRI assessed as severe by the CEC.

Finally based on EMA comments two additional exploratory endpoints were added to the analysis of the first RSV season.

In comparison to the immunogenicity analysis described in the CTP (Section 11.9.2) for all Revaccination Subcohorts (and not only for Revaccination Subcohort A with revaccination at day 365) geometric mean ratios and corresponding 95% CIs between Day 15 post first vaccination and Day 15 post second vaccination within the group receiving active study vaccine on Day 1 and

the day of the second vaccination depending on the Revaccination Subcohort will be calculated for the different assays.

Categorical BMI was updated to align with the Phase 3 studies to include the categories ‘< 18.5 kg/m^2’, ‘18.5 to < 25 kg/m^2’, ‘25 to < 30 kg/m^2’ and ‘>= 30 kg/m^2’. Additionally, smoking status was updated. Participants who use used nicotine patches or gum are no longer being considered as a smoker. Details were added to the analyses of analgesics and antipyretics to specify the period assignment if usage begins on day of vaccination.

The fourth sensitivity analysis in Section 4.4.2.2. was updated. The specificity for RSV A for the GenMark assay is 93%-96% and for RSV B its 95%-97% which might result in more false positives compared to GeneXpert (specificity of 99-100%). Therefore, the DDL results were used to determine RSV positivity of the ARI for cases where the results of GeneXpert and GenMark differ.

In comparison to the objectives and endpoints in the CTP, first occurrence of RT-PCR-confirmed RSV-mediated LRTD during the second, third, across the second and third and across all three RSV seasons will only be analysed according to Case Definition 1. Additionally, the efficacy endpoints will not be analysed across the first two RSV seasons, only across season 2 and 3 and across all three RSV seasons.

Following CBER comments and to align with the Phase 3 studies, the follow-up time during the RSV Seasons was updated to be defined as the time between 14 days post-vaccination and the occurrence of the first event, instead of as the time between vaccination and the occurrence of the first event. This update is not applied to the primary analysis (described in Section 3.1 and Section 4), but only to the end of efficacy study analysis (described in Section 3.6 and Section 5).

Details on the calculation of duration of an ARI episode were added to Section 4.4.2.1.3. to clarify the approach that was used during the Primary Analysis of the first RSV season. Additionally, a note was added to the description of determining a new onset or worsening to Section 4.4.2.1.1 to clarify the approach for RSV Season 2 and 3.

## **2. GENERAL ANALYSIS DEFINITIONS**

### **2.1. Study Phases**

A baseline (or reference) value for safety and immunogenicity will be defined as the value of the last available assessment prior to the first vaccination on Day 1. If there was no immunogenicity assessment done pre-vaccination, the assessment post-vaccination on Day 1 can be used as the baseline value for the immunogenicity analysis, if available.

A baseline (or reference) value for the efficacy analysis of the first RSV season will be defined as the worst value of the available assessment at Day 1 visit, if Day 1 visit is not available the Day 1 unscheduled visit closest to the day of vaccination will be used. In case two or more assessments are available at the same visit or at the same day of the selected baseline visit (for example assessments both at the eDiary and eDevice) the worst will be used (per question).

A new baseline (or reference) value for the efficacy analysis of the second and third RSV season will be defined as the worst value of the available assessment at Day 365/Day 730 visit, if Day 365/Day 730 visit is not available the Day 365/Day 730 unscheduled visit closest to the relative day 365/day 730 will be used. In case no Day 365/Day 730 visit (schedule or unscheduled) is available then the baseline of the first/second (or first) RSV season will be used. In case two or more assessments are available at the same visit or at the same day of the selected baseline visit (for example assessments both at the eDiary and eDevice) the worst value will be used (per question).

The safety analysis will present all results by period, unless specified otherwise. Immunogenicity results will be presented per analysis time point (see Section 2.1.2) as appropriate. Listings will be shown per phase, period and time point. Efficacy results will be presented across the entire season or per timepoint, where appropriate.

Study day or relative day is defined as follows:

Study Day = visit date - date of Day 1 + 1; if visit date > date of Day 1 (date of first vaccination).

Study Day = visit date - date of Day 1; if visit date < date of Day 1 (date of first vaccination).

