#### **New onset or worsening of symptoms:**

To determine new onset or worsening of symptoms, symptoms should be compared with the respective baseline of the season wherein the episode started:

- Clinical assessment by the site staff will be compared with clinical assessment baseline by the site staff.
- Patient reported outcomes reported on the site's eDevice and on the participants eDiary will be compared with the baseline patient reported outcomes.

Symptoms present during an ARI episode but not at the baseline assessment will be considered as symptoms with a new onset. Symptoms present at the baseline assessment that become worse (higher severity) during the ARI episode will be considered as worsening symptoms.

For assessments that are numerically scored (Decreased oxygen, tachypnea, and fever) new onset or worsening is defined as follows:

- Decreased oxygen saturation is defined as:
  - oxygen saturation of  $<90\%$  for participants with a baseline oxygen saturation of  $\geq 90\%$  or a missing baseline at randomization (new onset)
  - for participants with baseline oxygen saturation  $<90\%$ , decreased oxygen saturation is defined as a  $\geq 3\%$  decrease in their oxygen saturation from baseline (worsening).
- Tachypnea is defined by respiratory rate (RR)  $>20$  breaths per minute:
  - For subjects with baseline RR  $\leq 20$  or a missing baseline, a value  $>20$  is considered a new onset.
  - For subjects with baseline RR  $>20$  (and  $\leq 25$ ), a value  $>25$  is considered a worsening.
- Fever: all temperatures  $>37.8^{\circ}\text{C}$  during an ARI episode will be considered as a fever, regardless of the baseline temperature of the participant. For example, if a subject has baseline temperature of 37.9 degrees Celsius and during the ARI episode his temperature of is again 37.9 degrees Celsius, it will be counted as a systemic symptom of fever.

Note 1: Shortness of breath and respiratory effort reported at the clinical assessment form will not be taken into account for the case definitions.

Note 2: If a participant at the clinical assessment reported a new onset or worsening of dyspnea and had decreased oxygen saturation, then it counts only as one symptom towards the case definitions. Similarly, if a participant had a new onset or worsening of wheezing and rhonchi, rales or other sign of consolidation, it also counts as one symptom.

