**Counting of symptoms during an ARI episode:**

Counting of the number of symptoms with new onset or worsening will be done per day and per assessment (clinical assessment or patient reported outcome in the eDiary or in the eDevice). Therefore, if a subject has several assessments at the same day (e.g. at ARI day 3-5, or by accident two RiiQs at the eDiary during the same day), the case definitions cannot be met by combining symptoms from different assessments, the required number of symptoms must be attained at one assessment.

For example, if at Day 3 a participant reports in the eDiary mild cough and the study staff reports mild wheezing at the same day, this participant does not meet case definition 2, because the 2 LRTI symptoms are reported by 2 different assessments. The participant would meet the case definition only if both symptoms were reported in the eDiary or if both were reported by the study staff in the clinical assessment.

Note: Patient reported outcomes reported in the eDiary and in the eDevice at the same day can be distinguished by the App type ID linked to the device and by the time of reporting.

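### The season 1 efficacy baseline has no pre-vaccination limit, so a post-dose entry on Day 1 could mask some Case Definition 3 cases and bias that VE modestly upward

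*SAP*

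**What the plan says.** SAP Section 2.1 gives two baselines close together.

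- **Safety and immunogenicity:** "the value of the last available assessment prior to the first vaccination on Day 1". One post-dose exception is written out, and it covers only a missing immunogenicity sample.
- **Season 1 efficacy:** "worst value of the available assessment at Day 1 visit, if Day 1 visit is not available the Day 1 unscheduled visit closest to" (vaccination day is the reference point). The rule continues: "In case two or more assessments are available at the same visit or at the same day of the selected baseline visit", with the two participant-facing devices as the illustration ("for example assessments both at the eDiary and eDevice) the worst will be used (per question"). Nothing requires the assessment to precede the dose.

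Section 4.4.2.1.1 then uses this baseline to count symptoms. "Patient reported outcomes reported on the site's eDevice and on the participants eDiary will be compared with the baseline patient reported outcomes". A symptom absent at baseline counts as new onset. For one already present, "Symptoms present at the baseline assessment that become worse (higher severity) during the ARI episode will be considered as worsening symptoms". Measured temperature is exempt: a reading above the threshold "will be considered as a fever, regardless of the baseline temperature of the participant".

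Under Tables 6 and 7, Case Definitions 1 and 2 use only lower respiratory symptoms. Case Definition 3 can also be met by one lower respiratory symptom plus one systemic symptom (fatigue/malaise, fever or feverishness). Under Section 4.4.2.2, success on any one of the three primary endpoints demonstrates proof of concept.

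**The concern.** A baseline used to decide whether a case has occurred should not depend on the treatment. A value recorded after the injection can be a treatment effect, and taking the worst value means that such an entry can only raise the baseline. Fatigue and feeling feverish are typical same-day vaccine reactions, and both are qualifying systemic symptoms for Case Definition 3. If a participant's baseline is raised in this way, the same symptom at the same grade during a later RSV episode no longer counts. Where this happens more often on active vaccine than on placebo, active-arm cases are lost in excess and VE for Case Definition 3 is overstated.

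Other outputs share the exposure: RiiQ total scores that contain systemic items, with their AUCs of change from baseline (Section 4.5.1); the PGI-H change from baseline (Section 4.5.2.1); and exploratory Case Definitions 1a and 2a, to the extent that feeling feverish is read there against baseline (Section 4.4.4.1).

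**Working it through.** **1. Can a post-dose entry reach the baseline?** The SAP does not say when on Day 1 the RiiQ is completed. Section 4.15 counts ARI surveillance from the day of vaccination inclusive, and Section 4.4.2.1.1 has participants complete the RiiQ daily on the eDiary once an ARI is open. An episode opened on Day 1 would therefore put a home entry on the same day as the baseline visit, and the rule would keep it where it is worse. So the text admits a post-dose value; how often one occurs is not given.

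**2. Which endpoints are exposed?**

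| Component | Exposed? | Why |
|---|---|---|
| Case Definitions 1 and 2 | Not plausibly | Lower respiratory symptoms only |
| Respiratory rate, oxygen saturation | No | Collected before vaccination (Section 4.2.2) |
| Measured fever | No | Counts whatever the baseline |
| RiiQ fatigue, feeling feverish (Case Definition 3) | Yes | Compared with the participant-reported baseline |

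**3. Share of Case Definition 3 cases that depend on a systemic symptom.** The worked example at the end of Section 4.4.1.1 has 18 events under Case Definition 2 and 25 under Case Definition 3: (25 − 18)/25 = 7/25 = 28%. This is an illustrative split pooled over both arms, not data.

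**4. Bias in VE.** Let d be the net excess fraction of the active arm's systemic-dependent cases that are masked (an assumption; the SAP gives no figure). Then f = 0.28 × d, and observed VE = 1 − (1 − VE)(1 − f).

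| d (assumed) | f | True VE 0% reads as | True VE 70% reads as |
|---|---|---|---|
| 0 | 0 | 0% | 70% |
| 10% | 2.8% | 2.8% | 1 − 0.30 × 0.972 = 70.8% |
| 20% | 5.6% | 5.6% | 1 − 0.30 × 0.944 = 71.7% |
| 30% | 8.4% | 8.4% | 1 − 0.30 × 0.916 = 72.5% |

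**5. One-sided type I error for Case Definition 3.** Take the example's cut-off of 0.0175. With 1:1 allocation and no true effect, the active-arm share of cases is p = (1 − f)/(2 − f). The exact binomial rejects at 6 or fewer active cases of 25, or at 17 or fewer of 50.

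| Case Definition 3 events | f = 0 | f = 2.8% | f = 8.4% |
|---|---|---|---|
| 25 (SAP example) | 0.0073 | 0.0089 | 0.0131 |
| 50 (assumed, same cut-off) | 0.0164 | 0.021 | 0.034 |

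At 25 events the discreteness of the exact test keeps the error below 0.0175 over this range. At 50 events it does not.

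**6. RiiQ change scores.** The total respiratory and systemic score is a mean of 13 items. Each systemic item raised by one grade at baseline lowers every later change score for that participant by 1/13 = 0.077.

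**The case against.** The strongest reply is that the route is undocumented. Section 4.4.2.1.1 places the home RiiQ inside an ARI episode. Outside episodes the home device asks one surveillance question twice a week. Post-dose solicited symptoms are collected only in the Safety Subset, and nothing says they feed the RiiQ baseline. The unscheduled-visit clause is only a fallback. The protocol, which is not shown, may place every Day 1 questionnaire before the dose. This stands as a limit on frequency: no figure in the SAP supports 10-30%, and the true figure may be zero. It does not remove the gap, because the rule as written would keep a worse post-dose entry.

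A Case Definition 3 case also has several ways to survive masking. Measured fever counts regardless of baseline, site-assessed malaise is compared with a separate staff baseline, and one qualifying assessment in the episode is enough. That is correct. It means d must be read as cases lost after all these routes fail, which makes the upper end of the range harder to reach.

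Section 4.4.2.2 includes a sensitivity analysis using only clinical-assessment symptoms, which bypasses the participant-reported baseline. It helps, but it also changes the source of the endpoint. The participant-reported-only analysis reuses the same baseline, and no listed analysis varies it.

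A reader might infer that contamination occurs in the active arm alone, that VE is inflated on all primary endpoints, or that every RiiQ score is distorted. The document supports none of these. Placebo is also injected and the study is double-blind, so only the between-arm excess biases VE. Case Definitions 1 and 2 contain no systemic symptom. The RiiQ respiratory and lower respiratory scores contain no systemic items.

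**Conclusion.** The point holds in a limited form. Section 2.1 omits, for season 1 efficacy, the pre-dose condition it applies to safety and immunogenicity, and combines that omission with a worst-value rule. The result is a possible upward bias in VE for Case Definition 3, conditional on post-dose RiiQ entries on Day 1. On the SAP's illustrative 28% share and an assumed net masking of 10-30% of the active arm's systemic-dependent cases, it is 2.8 to 8.4 percentage points at a true VE of 0%, and about 0.8 to 2.5 points at 70%. It is zero if all Day 1 entries are pre-dose. The document does not show that any bias occurred. The exposed change-from-baseline PRO outputs and exploratory definitions 1a and 2a carry the same conditional risk, which is not quantified here beyond the per-item arithmetic.

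**What to change.** Restrict the season 1 efficacy baseline to assessments time-stamped before the first vaccination, take the worst answer per question only among those, and accept an unscheduled visit only if it precedes the dose. The data should allow this: the time of first vaccination starts the post-dose period in Table 2, and Section 4.4.2.1.1 notes that same-day eDiary and eDevice reports "can be distinguished by the App type ID linked to the device and by the time of reporting".

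Section 1.6 refers to the season 1 primary analysis as already carried out, so this should not replace its baseline after the fact. Add it as a sensitivity analysis of Case Definition 3 and of the change-from-baseline PRO scores. Report by arm how many participants have a post-dose entry in their Day 1 baseline, and how many have only a post-dose one. Show results with the post-dose-only baselines both kept and set to missing. If the counts are zero, one sentence saying so closes the point.

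The cost is a time filter, a count table and a rerun of existing models. The downside is that a few participants would have no pre-dose baseline. Section 4.4.2.1.1 treats a missing baseline as no symptoms at all, so a chronic cough or wheeze in these participants would count as new onset under every case definition. That is why both versions should be shown.
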